12.7. The Columbia-Suicide Severity Rating Scale

The C-SSRS, investigator administered version, was designed to provide a prospective, standardized measure of suicidality. The scale allows clinicians and researchers alike to assess the severity and lethality of suicidal behaviors and ideations and can be used to monitor treatment outcomes and establish suicide risk in a variety of research and clinical settings. Requiring approximately 5 min for completion, the C-SSRS is administered in the form of a clinical interview. This C-SSRS is available in 3 versions:

For this study we are using the following versions: For screening: Lifetime/Recent version and for the remaining part of the study: Since Last Visit version.

C-SSRS will be collected at different time points as per the SoA in Protocol Section 9.

The C-SSRS categories have been re-ordered from the actual scale to facilitate the definitions of the endpoints, and to enable clarity in the presentation of the results: Category 1 – Wish to be Dead, Category 2 – Non-specific Active Suicidal Thoughts, Category 3 – Active Suicidal Ideation with Any Methods (Not Plan) without Intent to Act, Category 4 – Active Suicidal Ideation with Some Intent to Act, without Specific Plan, Category 5 – Active Suicidal Ideation with Specific Plan and Intent, Category 6 – Preparatory Acts or Behavior, Category 7 – Aborted Attempt, Category 8 – Interrupted Attempt, Category 9 – Actual Attempt (non-fatal), Category 10 – Completed Suicide.

Suicidal ideation is defined as a "yes" answer at any time during treatment to any one of the five suicidal ideation questions (Categories 1-5) on the C-SSRS. Suicidal behavior is defined as a "yes" answer at any time during treatment to any one of the five suicidal behavior questions (Categories 6-10) on the C-SSRS. Suicidal ideation or behavior is defined as a "yes" answer at any time during treatment to any one of the five suicidal behavior at any time during treatment to any one of the ten suicidal ideation and behavior questions (Categories 1-10) on the C-SSRS.

A summary table presenting number of patients with suicidal ideation, suicidal behavior, and self-injurious behavior without suicidal intent will be generated, as well as a shift table to demonstrate changes in C-SSRS suicidal ideation scores from baseline to all post-baseline visits by treatment. Patients with suicidal ideation, suicidal behavior, or self-injurious behavior without suicidal intent based on the C-SSRS will be listed.

13. Interim Analyses

No interim analysis is planned in this study.

14. Changes from Analysis Planned in Protocol

The randomized population is not specified in protocol, but this population is added for listings and disposition summaries.

Exploratory endpoint added: Patients achieving 100% reduction in EASI (EASI100) response at Weeks 2, 4, 8, 12, 16, and 20.

15. Reference List

16. **Programming Considerations**

Computer-generated TFL output will adhere to the following specifications.

All TFLs, and statistical analyses will be generated using SAS for Windows, Release 9.4 (SAS Institute Inc., Cary, NC, USA).

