### 4.3.2 Monitoring of Cardiovascular, Psychiatric, Hepatic, and Metabolic Risks

In the unblinded phase 2 trial UNI50001-203 (under reporting) in psoriasis, seven cases of elevated ALT were observed, and one patient in the orismilast 40 mg group had self-injurious behavior without suicidal intent at week 16. No deaths or serious infections were reported in UNI50001-203. Hepatic laboratory parameters will be monitored. All patients will be monitored for any cardiovascular manifestations using vital signs and 12-lead ECG at scheduled visits. Drug class potential effects, such as weight loss and major depression, will be monitored during the study. Patients with major depression, presenting major psychiatric disorders or at risk for suicide will be excluded from enrollment, and suicidal ideation and depressive symptoms will be assessed in the course of the study by the Columbia-Suicide Severity Rating Scale (C-SSRS) and Hospital Anxiety and Depression Scale (HADS), respectively. Patients will be informed of the potential increased risk of depression or suicidal thoughts of this class of drugs, and recommended to promptly contact their study doctor in case of such event.

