## Table 4. Schedule of Assessments

	Screening		Follow-up						
Procedure	Between Day -28 and -7	Day 1 (Baseline)	W1 (±1 d) a, b	W2 (±1 d) a	W4 (±3 d) a	W8 (±3 d) a	W12 (±3 d) a	W16 (EOT/ET; ±3 d) a	W20 (±3 d) a or 4 weeks after EOT/ET; ±3 d a
Informed consent (before any study procedures)	Х								
Demography	Х								
Medical history, including medications, alcohol consumption, and smoking history (last 6 months)	Х								
Concurrent medication review	Х	Х	Х	Х	Х	Х	Х	Х	Х
Inclusion and exclusion criteria review	X	Х							
Physical examination c	X	Х			Х	Х	Х	Х	Х
12-lead ECG (single measurement)	X				Х	Х		Х	
Vital signs d	X	Х			Х	Х	Х	Х	Х
Weight	Х	Х			Х	Х	Х	Х	Х
Height		Х							
BMI		Х				Х		Х	Х
Randomization		Х							
Adverse events	X	Х	Х	Х	Х	Х	Х	Х	Х
Blood sample for serology (HIV antibody, HBV, HCV, HBsAg, HBcAb, HBsAb)	Х								
Safety laboratory assessments (hematology, serum chemistry, urinalysis)	X	X			Х	Х	Х	Х	
Pregnancy test e	Х	Х		Х	Х	Х	Х	Х	
Blood samples for drug and metabolite PK analysis: plasma levels		X			Х	Х		Х	
Optional: blood samples for drug PK profile					Х			Х	

This document is confidential.

	Screening		Treatment Period								
Procedure	Between Day -28 and -7	Day 1 (Baseline)	W1 (±1 d) a, b	W2 (±1 d) a	W4 (±3 d) a	W8 (±3 d) a	W12 (±3 d) a	W16 (EOT/ET; ±3 d) a	W20 (±3 d) a or 4 weeks after EOT/ET; ±3 d a		
Superficial skin sample using tape stripping f		Х						Х			
IGA-AD, BSA, and EASI assessments	X	Х		Х	Х	Х	Х	Х	Х		
Peak pruritus NRS, sleep disturbance NRS, and skin pain NRS		Х	Х	Х	Х	Х	X	Х	Х		
PGIS, PGIC		Х		Х	Х	Х	Х	Х	Х		
C-SSRS	Х	Х		Х	Х	Х	X	Х	Х		
DLQI		Х				Х		Х	Х		
POEM		Х		Х	Х	Х	X	Х	Х		
HADS		Х		Х	Х	Х	X	Х	Х		
Pulmonary status NRS g		Х			Х	Х	Х	Х	Х		
Dispense study drug		Х		Х	Х	Х	Х				
Collect study drug, including packaging				Х	Х	Х	Х	Х			
Compliance check			X h	Х	Х	Х	Х	Х			

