4.1. Brief Description

This multicenter, randomized, double-blind, placebo-controlled, parallel-group, Phase 2b dose-ranging study is designed to assess the efficacy and safety of modified-release orismilast compared with placebo in patients aged at least 18 years with moderate to severe AD. Efficacy and safety outcomes will be evaluated to select an appropriate orismilast dose for subsequent Phase 3 studies. The study will be conducted at approximately 48 centers in Europe and the United States.

After a Screening visit up to 28 days before Baseline, approximately 210 patients will be assigned randomly in a 1:1:1:1 ratio to receive 1 of the 3 orismilast doses (20 mg, 30 mg, or 40 mg) or placebo BID for 16 weeks, with a 4-week follow-up visit. Administration will begin at Baseline with a dose titration period of up to 2 weeks' duration depending on the dose level. The maximum duration of study participation for each patient is approximately 24 weeks.

Patients will be seen at the site at Screening, Baseline (Day 1), and Weeks 1, 2, 4, 8, 12, 16 (EOT visit), and 20 (Follow-up visit, 4 weeks after treatment completion or discontinuation). The visit at Week 1 can be conducted via a telemedicine procedure at the Investigator's discretion.

Patients who have been diagnosed with moderate to severe AD for a minimum of 1 year (before the Screening visit) using the Hanifin and Rajka criteria with affected BSA of at least 10%, Eczema Area and Severity Index (EASI) score of at least 16, and Investigator Global Assessment for Atopic Dermatitis (IGA-AD) grade of at least 3 at the screening and baseline visits will be included in the study. Patients must also have a documented history of inadequate response to treatment with topical medications given for at least 4 weeks (at least 2 weeks for high potency topical corticosteroids), or as labeled, or for whom topical treatments are otherwise medically inadvisable.

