5.5. Safety Endpoints

• The occurrence, severity, and seriousness of treatment-emergent AEs (TEAEs) reported over the 16week Treatment Period and the 4-week Follow-up Period.

- Changes from Baseline in physical examination findings; vital signs measurements (body temperature, respiration rate, heart rate, and systolic and diastolic blood pressure measurements); and body weight over the 16-week Treatment Period and the 4-Week Follow-up Period.
- Clinically significant abnormal changes in ECG findings over the 16-week Treatment Period.
- Changes from Baseline in safety laboratory values (hematology, serum chemistry, and urinalysis) over the 16-week Treatment Period.
- Change from Baseline in HADS score at each visit except Week 1.
- C-SSRS score at each visit except Week 1.

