7.2. Key Definitions

Treatment period

The Treatment Period for this study is 16 weeks, from Day 1 to Week 16 (112 ± 3 days).

Study day

If the event date \geq date of first dose of IP, study day = event date – date of first dose of IP + 1. If the event date < date of first dose of IP, study day = event date – date of first dose of IP.

Baseline Value

Baseline value will be defined as the last non-missing value recorded prior to the first intake of study treatment.

Change from Baseline (CFB)

CFB = Post-baseline value – Value at baseline

Percentage change from baseline (PCFB)

PCFB = ((Post-baseline value – Value at baseline) / Value at baseline)*100%.

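### The C-SSRS patient counts stop at the end of treatment, so suicidal behaviour first reported at the Week 20 visit is counted in no C-SSRS table

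*SAP*

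**What the plan says.** The safety endpoint in SAP 5.5, as in Protocol 5.2.3, is "C-SSRS score at each visit except Week 1". Table 4 of the protocol schedules the C-SSRS at Screening, Day 1 and Weeks 2, 4, 8, 12, 16 and 20. After screening the version in use asks about the time since the last visit (SAP 12.7).

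SAP 12.7 then defines the terms to be counted. For ideation: "Suicidal ideation is defined as a 'yes' answer at any time during treatment to any one of the five suicidal ideation questions (Categories 1-5"). For behaviour, the yes must come "at any time during treatment to any one of the five suicidal behavior questions (Categories 6-10) on the C-SSRS". The combined term has the same limit.

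SAP 7.2 gives the period: "The Treatment Period for this study is 16 weeks, from Day 1 to Week 16 (112 ± 3 days"). SAP 4.1 describes Week "20 (Follow-up visit, 4 weeks after treatment completion or discontinuation").

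Three C-SSRS outputs are planned:

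- Table 14.3.4.4.5: patients with ideation, behaviour, or self-injurious behaviour without suicidal intent.
- Table 14.3.4.4.6: a "shift table to demonstrate changes in C-SSRS suicidal ideation scores from baseline to all post-baseline visits by treatment".
- Listing 16.2.8.2.6: patients in any of the three groups.

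**The concern.** The endpoint includes Week 20 and the data are collected there, but the definitions that feed the main count exclude it. The exclusion does not look deliberate. In SAP 5.5 the ECG and laboratory endpoints are expressly limited to the 16-week Treatment Period, and the C-SSRS endpoint is not. SAP 14, which lists changes from the protocol, does not mention a narrower C-SSRS window. Protocol 14 says the SAP prevails where the two differ, so the narrower rule would govern.

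Protocol 4.3.2 names depression and suicidal thoughts as a possible class effect to be monitored. With few events expected in about 210 patients, one uncounted patient could change how the table reads. The Week 20 assessment is the scheduled one that covers the weeks after stopping drug.

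**Working it through.** The plan gives no figure to reproduce. The check is whether Week 20 can fall inside the counting window, and which outputs pick it up if it does not.

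**1. Window arithmetic for a patient who completes treatment** (inputs: SAP 7.2; Table 4 visit windows)

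- Latest end of the Treatment Period: 112 + 3 = day 115.
- Week 20 = 20 × 7 = day 140; it opens at 140 − 3 = day 137 and closes at 140 + 3 = day 143.
- Gap: 137 − 115 = 22 days at least.
- Table 4 also allows the visit to be timed from end of treatment (4 weeks ± 3 days). With the earliest end of treatment, 112 − 3 = day 109, it opens at 109 + 28 − 3 = day 134, still 134 − 115 = 19 days outside.

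**2. Assessments counted**

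| Scheduled visit | Days | Inside the Treatment Period? |
|---|---|---|
| Week 2 | 13–15 | yes |
| Week 4 | 25–31 | yes |
| Week 8 | 53–59 | yes |
| Week 12 | 81–87 | yes |
| Week 16 | 109–115 | yes |
| Week 20 | 137–143 | no |

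Five of six scheduled post-baseline assessments count and one does not.

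**3. Comparison with the adverse event window.** SAP 12.1 treats an event as treatment-emergent up to 7 days after the last dose: to day 112 + 7 = 119, or at the latest 115 + 7 = 122. Suicidal behaviour 3 days after the last dose falls after the Week 16 visit, so the C-SSRS first captures it at Week 20. It would be a TEAE, yet would not count as suicidal behaviour in Table 14.3.4.4.5. Two safety outputs would then disagree about one event.

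**4. Where a first positive at Week 20 appears**

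| Output | Ideation | Behaviour |
|---|---|---|
| Table 14.3.4.4.5 (patient counts) | no | no |
| Table 14.3.4.4.6 (shift, ideation per the text of SAP 12.7) | yes | no |
| Listing 16.2.8.2.6 | window not stated | window not stated |
| Follow-up AE table 14.3.1.13 and AESI listing | if recorded as an AE | if recorded as an AE |

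**5. Early stoppers.** Protocol 7.4 asks for the Week 16 assessments at discontinuation and a follow-up visit within 4 weeks, and then offers the remaining visits off drug. As an illustration, take a patient who stops at Week 4, has the follow-up at about Week 8, and stays for Weeks 12, 16 and 20. If *during treatment* means the calendar period, Weeks 2, 4, 8, 12 and 16 count (5 of 6). If it means time on drug, only Weeks 2 and 4 count (2 of 6). The SAP does not choose between them.

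**The case against.** The best defence is that little is lost. Ideation at Week 20 is in the shift table. Protocol 11.8.1 collects adverse events until the follow-up visit, and Protocol 11.8.2 makes suicidal ideation or behaviour recorded as an AE an AESI. SAP 12.1 plans tables of AEs and SAEs starting in the follow-up period and a separate AESI listing. SAP 7.1 says all data will be listed, and the safety analysis is descriptive only. All of this stands. It limits the point to the C-SSRS counts but does not close the gap: the shift table does not cover behaviour under the text of SAP 12.7, the AESI table is limited to treatment-emergent events, and an AE table by preferred term does not replace the prespecified C-SSRS count.

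A reader might infer three stronger things that the documents do not support:

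- That a Week 20 event would appear in no table at all. The AE outputs above contradict this.
- That early stoppers necessarily lose further visits. Under the calendar definition in SAP 7.2, their off-drug visits up to Week 16 are counted.
- That the psoriasis trial shows this rule hiding an event. Protocol 4.3.2 reports that "one patient in the orismilast 40 mg group had self-injurious behavior without suicidal intent at week 16". Week 16 is inside the Treatment Period, and that type of event falls under none of the three definitions and has no stated window. The case shows why the topic matters, not that the rule would have missed it.

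**Conclusion.** The counting rule in SAP 12.7 is wrong as written, because it contradicts the endpoint it is meant to summarise. For completers it drops 1 of 6 scheduled post-baseline assessments from Table 14.3.4.4.5, and suicidal behaviour first reported at Week 20 has no C-SSRS tabulation.

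This rests on reading *during treatment* by the SAP's own Treatment Period, or by time on drug, which gives the same result for completers. It also assumes a follow-up visit held on schedule; Protocol 6.3 lets it be brought forward when new treatment is needed. For early stoppers the size is undetermined until the term is defined. The documents do not allow the number of affected patients to be computed.

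**What to change.** In SAP 12.7:

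1. In all three definitions (ideation, behaviour, either), replace *during treatment* with *at any post-baseline assessment through Week 20*.
2. In Table 14.3.4.4.5, show treatment-period and follow-up counts separately. Define the boundary for patients who stop early, including visits attended off drug.
3. Apply the same window to self-injurious behaviour without suicidal intent and to Listing 16.2.8.2.6.

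The cost is a wording change and a split by period in one table and its shell. No new data, visits or procedures are needed.

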16.1. General Considerations

- A separate SAS program will be created for each output
- Each output will be stored in a separate file
- Output files will be delivered in Word format and portable document format (pdf)
- Numbering of TFLs will follow ICH E3 guidance

16.2. Table, Figure, and Listing Format

16.2.1. General

- All TFLs will be produced in landscape format on A4 paper size, unless otherwise specified
- All TFLs will be produced using the Courier New font, size 8 which is the smallest acceptable point size for the Regulatory Authorities
- The data displays for TFLs will have a minimum blank 1-inch margin on all 4 sides.
- Headers and footers for figures will be in Courier New font, size 8 which is the smallest acceptable point size for the Regulatory Authorities
- Legends will be used for all figures with more than one variable, group, or item displayed
- TFLs will be in black and white (no color), unless otherwise specified
- Specialized text styles, such as bolding, italics, borders, shading, and superscripted and subscripted text, will not be used in the TFLs, unless otherwise specified. On some occasions, superscripts 1, 2, or 3 may be used (see below)
- Only standard keyboard characters will be used in the TFLs. Special characters, such as nonprintable control characters, printer-specific, or font-specific characters, will not be used. Hexadecimal-derived characters will be used, where possible, if they are appropriate to help display math symbols (e.g., μ). Certain subscripts and superscripts (e.g., cm2, Cmax) will be employed on a case-by-case basis
- Mixed case will be used for all titles, footnotes, column headers, and programmer-supplied formats, as appropriate

16.2.2. Headers

- All output will have the following header at the top left of each page:
- UNION therapeutics A/S Protocol UNI50001-202 (Syneos Health study number 7025424)

- Draft/Final Run <date>
- All output will have Page n of N at the top or bottom right corner of each page. TFLs are internally paginated in relation to the total length (i.e., the page number will appear sequentially as page n of N, where N is the total number of pages in the table)
- The date the output was generated will appear along with the program name as a footer on each page

16.2.3. Display Titles

• Each TFL will be identified by the designation and a numeral. (i.e., Table 14.1.1). A decimal system (x.y and x.y.z) are used to identify TFLs with related contents. The title will be centered. The analysis population will be identified on the line immediately following the title and will be enclosed in parenthesis. The title and table designation will be single spaced. A solid line spanning the margins will separate the display titles from the Column headers. There will be one blank line between the last title and the solid line.

Table x.y.z First Line of Title Second Line of Title if Needed (Safety population)

16.2.4. Column Headers

- Column headings will be displayed immediately below the solid line described above in initial upper-case characters.
- In the case of efficacy tables, the variable (or characteristic) column is on the far left followed by the treatment group columns and total column (if applicable). P-values may be presented under the total column or in separate p-value column (if applicable). Within-treatment comparisons may have p-values presented in a row beneath the summary statistics for that treatment
- For numeric variables, include 'unit' in column or row heading when appropriate
- Analysis population sizes will be presented for each treatment group in the column heading as (N=xx) (or in the row headings, if applicable). This is distinct from the 'n' used for the descriptive statistics representing the number of patients in the analysis population
- The order of treatments in the tables and listings will be Placebo first.

16.2.5. Body of the Data Display

16.2.5.1. General Conventions

Data in columns of a table or listing are formatted as follows:

- Alphanumeric values will be left-justified;
- Whole numbers (e.g., counts) will be right-justified; and

• Numbers containing fractional portions will be decimal aligned.

16.2.5.2. Table Conventions

- Units will be included where available
- For categorical parameters, all categories will be presented in the table, even if n=0 for all treatment groups in a given category. For example, the frequency distribution for symptom severity would appear as:

Severity	Ν
Rating	
severe	0
moderate	8
mild	3

Where percentages are presented in these tables, zero percentages will not be presented and so counts of 0 will be presented as 0 and not as 0 (0%).

- An Unknown or Missing category will be added to each parameter for which information is not available for 1 or more patients
- Unless otherwise specified, the estimated mean and median for a set of values will be printed out to 1 more significant digit than the original values, and standard deviations will be printed out to 2 more significant digits than the original values. The minimum and maximum will report the same significant digits as the original values. For example, systolic blood pressure will be presented as follows:

n	XXX
Mean (SD)	xx.x (x.xx)
Median	XX.X
Min, Max	Xx, xx

- P-values will be output in the format: '0.xxx', where xxx is the value rounded to 3 decimal places. Every p-value less than 0.001 will be presented as <0.001. If the p-value are less than 0.0001, then present as <0.0001. If the p-value is returned as >0.999, then present as >0.999
- Percentage values will be printed to one decimal place, in parentheses with no spaces, one space after the count (e.g., 7 (12.8%), 13 (5.4%)). Unless otherwise noted, for all percentages, the number of patients in the analysis population for the treatment group who have an observation will be the denominator. Percentages after zero counts will not be displayed and percentages equating to 100% will be presented as 100%, without decimal places
- Tabular display of data for medical history, prior/concomitant medications, and all tabular displays of adverse event data will be presented by the body system, treatment class, or SOC with the highest occurrence in the active treatment group in decreasing order, assuming all terms are coded. Within the body system, drug class and SOC, medical history (by preferred term), drugs (by ATC3 level), and adverse events (by preferred term) will be displayed in decreasing order. If incidence for more than 1 term is identical, they will then be sorted alphabetically. Missing descriptive statistics or p-values which cannot be estimated will be reported as '-'

- The percentage of patients will normally be calculated as a proportion of the number of patients assessed in the relevant treatment group (or overall) for the analysis population presented. However, careful consideration is required in many instances due to the complicated nature of selecting the denominator, usually the appropriate number of patients exposed. Details will be described in footnotes or programming notes, as necessary
- For categorical summaries (number and percentage of patients) where a patient can be included in more than one category, a footnote or programming note will be added describing whether the patient is included in the summary statistics for all relevant categories or just 1 category as well as the selection criteria
- Where a category with a subheading (such as system organ class) has to be split over more than one page, output the subheading followed by '(cont)' at the top of each subsequent page. The overall summary statistics for the subheading should only be output on the first relevant page

